## **2.2 PRETREATMENT EVALUATION**

- 2.2.1** Baseline testing and evaluations that do not impact eligibility
  - 2.2.1.1** Baseline MDASI-SP or MDASI-BT questionnaire (Appendix **12.7** or **12.8**).
  - 2.2.1.2** Total protein, albumin, calcium, phosphorus, glucose, BUN, uric acid, alkaline phosphatase, LDH, and when appropriate, anticonvulsant levels will be performed prior to initiation of treatment.
  - 2.2.1.3** PT, PTT and INR (obtained only on patients receiving warfarin therapy).
- 2.2.2** Baseline testing and evaluations that do impact eligibility.
  - 2.2.2.1** H&P to include prior therapy for the current cancer, blood pressure, Concurrent Medications, KPS and Neurologic examination within 14 days prior to registration.
  - 2.2.2.2** Brain or spine MRI within 14 days prior to registration. Patient must be on a steroid dose that has been stable or decreasing for at least 5 days. If the steroid dose is increased between the date of imaging and registration, a new baseline MRI is required.
  - 2.2.2.3** **NOTE:** Residual disease following resection of recurrent tumor is not mandated for eligibility into the study. To best assess the extent of residual disease post-operatively, an MRI should be done no later than 96 hours in the immediate postoperative period or at least 4 weeks postoperatively, within 14 days prior to registration. If the "within 96-hour of surgery" scan is more than 14 days before registration, the scan needs to be repeated
  - 2.2.2.4** Baseline Cardiac Testing to be performed within 14 days prior to registration includes:
    - EKG.
    - Echo or MUGA scan (MUGA preference as clinically indicated). These studies must be performed under the supervision of an experienced cardiologist, presumably at the same high-volume laboratory for the duration of the trial. The method used for LVEF assessment in an individual subject must be the same

throughout the trial. The guidelines of the American Society of Echocardiography will be used. These guidelines can be located on the www at <http://www.asecho.org/Guidelines.php>.

**2.2.2.5** Baseline Laboratory examinations to be conducted within 14 days prior to registration include:

- CBC with Differential and Platelets.
- Chemistries to include: SGPT (ALT), bilirubin, serum creatinine.
- Serum Pregnancy Test: Beta-HCG in women with childbearing potential.

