 To be obtained at pre- study. Timing for obtaining consent is not limited to “within 14 days of study registration”.

 Labs (chemistry, coagulation and hematology) does not have to be repeated prior to Cycle 1 as long as it is obtained within 14 days of start of treatment date.

Patients on post protocol lapatinib must have follow-up visit and MRI or CT scan every 2 months.

---

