- In addition, any subject who develops clinical signs and symptoms of cardiac failure should undergo an LVEF assessment and ECG.

3.7.8 After enrollment on the clinical trial, patients will complete as baseline measures the MDASI-BT or MDASI-SP. The patient will continue to complete the MDASI-BT and/or MDASI-SP at the time of clinical evaluation with MRI as long as the clinical therapy is being administered, unless clinical deterioration makes self-report not possible before that time. The time when patients are unable to complete the self report questionnaires will be used as part of the study analysis. The MDASI-BT and/or MDASI-SP will be completed only by the patient, unless changes in vision or weakness make this difficult. If this occurs, then the caregiver or research assistant may read the questions to the patient or assist with marking the severity number or score as described by the patient. A patient caregiver may complete the questionnaires as a patient-preference proxy if the patient’s deficits preclude self report.

3.7.9 Off treatment follow-up will continue on the following schedule until the patient meets off study criteria.

3.7.9.1 For patients with stable disease or response, MRI surveillance should continue every 2 months for 1 year after treatment completion, then every 3 months for 1 year, then every 4 months for 1 year, then every 6 months until progressive disease is noted, death or lost to follow-up.

3.7.9.2 Patients removed from study treatment for disease progression or treatment-related toxicity should continue to be followed with quarterly (every 3 month) updates of treatment regimens, disease status and survival.

3.7.9.3 Stable disease (SD) patients who develops progression while being followed on the “off treatment follow-up schedule”, will continue with follow-up requirements on the PD off treatment follow-up schedule, until patient meets off study criteria.

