## **3.8 CRITERIA FOR REMOVAL FROM PROTOCOL THERAPY AND OFF STUDY CRITERIA**

### **3.8.1 Criteria for Removal from Protocol Therapy**

A genuine effort must be made to determine the reason(s) why a patient fails to return for the necessary visits or is discontinued from the trial. Information regarding the reason for not completing the trial will be recorded on the appropriate case report forms.

It will be documented whether or not each patient completed the clinical study. If for any patient study treatment or observations were discontinued the reason will be recorded on the appropriate case report form. Reasons that a patient may discontinue participation in a clinical study are listed below:

Any patient who receives at least one dose of trial medication will be included in the safety analysis.

- 3.8.1.1** Evidence of recurrent or progressive disease
- 3.8.1.2** Second malignancy
- 3.8.1.3** Development of unacceptable toxicity during treatment
- 3.8.1.4** Non-adherence to the protocol
- 3.8.1.5** Refusal of therapy
- 3.8.1.6** Pregnancy
- 3.8.1.7** At 2 years of protocol therapy

**3.8.2** Off Study Criteria

- 3.8.2.1** Death
- 3.8.2.2** Lost to follow-up
- 3.8.2.3** Withdrawal of consent for continued follow-up
- 3.8.2.4** Protocol defined follow-up completed
- 3.8.2.5** Withdrawal of consent

**3.8.3** Off study procedure

*For participating CERN sites:*

When a subject is taken off-study, notify CCR study coordinator via encrypted email.  
([name] email: [[contact]](mailto:[contact]) )

**3.8.4** POST PROTOCOL THERAPY AND FOLLOW UP

**3.8.4.1** Post Protocol Single Agent Lapatinib

Patients that are showing sustained Complete Response (CR), Partial Response (PR) or Stable Disease (SD) may continue Post protocol single agent therapy with lapatinib. Post protocol lapatinib supply may be obtained through Glaxo Smith-Kline (GSK), using the same drug ordering mechanism as detailed in section 10.2.12 (Agent Ordering/Requests).

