### **3.8.4.2 Post Protocol Follow Up**

Patients on post protocol single agent lapatinib will have follow up visits every 2 months for survival assessment and radiographic evaluation of disease per MRI or CT scan.

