## **6.2 RESPONSE CRITERIA**

6.2.1 The primary endpoint is median progression-free survival. A combination of the neurological examination and MRI brain scan will be used to define progression. Due to improvements in neuroimaging and the fact that tumor growth in certain regions of the CNS is without immediate neurologic signs and symptoms, greater reliance is placed on neuroimaging to define progression.

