6.2.2 Definitions of Response

6.2.2.1 **Measurable Disease:** Bi-dimensionally measurable lesions with clearly defined margins by MRI scan.

6.2.2.2 **Objective Status, To Be Recorded at Each Evaluation:** If there are too many measurable lesions to measure at each evaluation, choose the largest two to be followed before a patient is entered on study. The remaining lesions will be considered evaluable for the purpose of objective status determination. Unless progression is observed, objective status can only be determined when ALL measurable and evaluable sites and lesions are assessed.

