6.2.3 Response Criteria

6.2.3.1 **Stable/No Progression:** No evidence of new measurable lesions on MR imaging. The designation of Stable/No Progression requires a minimum of 12 weeks duration. All measurable and evaluable sites must be assessed using the same techniques as baseline.

6.2.3.2 **Partial response:**  $\geq 50\%$  reduction in the sum of products of all measurable lesions over baseline sum observed using the same techniques as baseline. The patient must be on a stable or decreased dose of corticosteroids to be evaluable for response.

6.2.3.3 **Complete response:** Complete resolution of all lesions. The patient cannot be on any corticosteroids with the exception of adrenal replacement doses.

6.2.3.4 **Progression:** 25% increase in the sum of products of all measurable lesions over smallest sum observed (over baseline if no decrease) using the same techniques as baseline, OR clear worsening of any evaluable disease, OR appearance of any new lesion/site, OR failure to return for evaluation due to death or deteriorating condition (unless clearly unrelated to this cancer).

6.2.3.5 **Unknown:** Progression has not been documented and one or more measurable or evaluable sites have not been assessed.

6.2.4 **Neurologic Function Score:** This method of neurologic evaluation notes the presence or absence of neurologic symptoms. This examination should coincide with objective measurement in tumor size.

0	No neurologic symptoms
1	Minor neurologic symptoms
2	Moderate neurologic symptoms – fully active
3	Moderate neurologic symptoms – less than fully active
4	Severe neurologic symptoms

- 6.2.5 **Performance Status:** Patients will be graded according to Karnofsky Performance Status (KPS)
- 6.2.6 **Time to Treatment Failure:** From date of registration to the date of first observation of progressive disease, non-reversible neurologic progression or permanently increased steroid requirement (applies to stable disease only), death due to any cause, or early discontinuation of treatment.
- 6.2.7 **Survival:** From date of registration to date of death due to any cause
- 6.2.8 **NOTE: Steroids:** Steroid dosage will be carefully monitored and recorded during each course of therapy and steroid dosage changes will be considered before response determinations are made.

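### Event-free patients on post-protocol lapatinib may be followed by CT, although the size criterion for progression requires the baseline MRI technique

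*Combined protocol and SAP*

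**What the plan says.** Section 3.8.4.1 restricts the extension to patients whose disease is controlled: those with sustained complete response, partial response or "Stable Disease (SD) may continue Post protocol single agent therapy with lapatinib". Section 3.8.4.2 sets their imaging as "radiographic evaluation of disease per MRI or CT scan", and the Précis and 3.1 say the same. Footnote 11 of the study calendar repeats it: "Patients on post protocol lapatinib must have follow-up visit and MRI or CT scan every 2 months". In the calendar, that footnote sits on the row for gadolinium MRI of head and/or spine.

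Elsewhere the endpoint rests on MRI:

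- Baseline (2.2.2.2): "Brain or spine MRI within 14 days prior to registration".
- On treatment (3.7.3): MRI before every other cycle.
- Progression (6.2.1): "A combination of the neurological examination and MRI brain scan will be used to define progression".
- Measurable disease (6.2.2.1): "Bi-dimensionally measurable lesions with clearly defined margins by MRI scan".
- The 25% size limb (6.2.3.4): the increase is measured "using the same techniques as baseline, OR clear worsening of any evaluable disease", followed by new lesion and by deterioration or death as further routes.

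For patients with stable disease or response who are off treatment, 3.7.9.1 says "MRI surveillance should continue every 2 months for 1 year after treatment completion", at longer intervals after that.

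**The concern.** The patients offered CT are the ones whose progression-free survival clock is still running. No section censors them when post-protocol lapatinib starts, and no section says how a CT is to be read against an MRI baseline. In a patient with measurable residual disease, the size limb of the progression definition therefore cannot be applied as written at a CT visit.

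This matters because section 8 bases the primary inference on an exponential posterior that uses total follow-up time and total events. Long event-free patients contribute much of that time. If the choice of scanner changes whether or when progression is recorded, the estimated median depends partly on site preference. The error could go either way. A missed or late progression raises the median, and a change of modality that is mistaken for growth lowers it.

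**Working it through.** **1. Reproduce the plan's figure.** Inputs from section 8: N = 50, exponential times, prior Inverse Gamma(2, 17.6761), posterior Inverse Gamma(2 + events, 17.6761 + ln2 × total time), event-free patients censored at 48 months. Median 10th and 90th percentiles over 4,000 simulated trials:

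| True median | Plan | Recomputed |
|---|---|---|
| 10.5 months | 8.72, 12.50 | 8.75, 12.58 |
| 14 months | 11.52, 16.66 | 11.52, 16.75 |

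The limits reproduce. The plan's own calculation therefore counts events out to month 48, well past the end of protocol therapy.

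**2. How many patients could be affected.** The maximum of 24 cycles of 28 days (3.1) is 672 days, or 22.1 months. The share still event-free is S(t) = 0.5^(t/median).

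- Median 10.5: S(22.1) = 0.233, or 11.6 of 50 patients. Expected events from then to month 48: 50 × (0.2328 − 0.0421) = 9.5.
- Median 14: S(22.1) = 0.335, or 16.8 of 50 patients. Expected events: 50 × (0.3352 − 0.0929) = 12.1.

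These are upper limits, because lapatinib continuation is optional and so is CT.

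**3. Illustration: every later event dated 2 months late (assumed).** The exponential estimate is ln2 × total time / events. Adding d months to a share S of patients, with the number of events unchanged, raises it by about ln2 × d × S.

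- Median 10.5: 0.693 × 2 × 0.233 = 0.32 months (3.1%).
- Median 14: 0.693 × 2 × 0.335 = 0.46 months (3.3%).

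Simulation of the section 8 posterior, 3,000 runs per setting, with the assumed share of these patients affected:

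| Share affected | True 10.5 | True 14 |
|---|---|---|
| 100% | 10.43 to 10.77 | 13.82 to 14.29 |
| 50% | 10.48 to 10.65 | 13.81 to 14.07 |
| 25% | 10.49 to 10.57 | 13.84 to 13.95 |

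With entry staggered over the plan's stated 40 months and analysis at month 48, the 100% case gives 10.45 to 10.70 and 13.87 to 14.27.

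**4. If the move came at 12 cycles (11.0 months).** S = 0.483 and 0.579, and the same formula gives 0.693 × 2 × 0.483 = 0.67 and 0.693 × 2 × 0.579 = 0.80 months. Section 3.4.2 gives an option to stop protocol treatment at that point. It does not mention moving to single-agent lapatinib.

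**5. Compare with precision.** The plan's 10th-to-90th percentile widths are 12.50 − 8.72 = 3.78 and 16.66 − 11.52 = 5.14 months. The shifts in step 3 are about 0.32/3.78 = 8% and 0.46/5.14 = 9% of those widths. In the same simulations the raw sample median did not move when only events after 22.1 months were affected.

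**The case against.** The strongest case on the other side has four parts.

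- **CT visits are not blind.** A reader might infer that a CT visit cannot be scored and becomes Unknown under 6.2.3.5. The documents do not say so. That category applies where sites were not assessed, and a CT does assess them. New lesion, clear worsening, and deterioration or death carry no technique condition, and 6.2.1 also uses the neurological examination. For patients in complete response, or enrolled without residual disease (2.1.1.11), imaging progression would normally be a new lesion. This stands, and it limits the gap to the size limb in patients with measurable residual disease.
- **Direction.** A reader might infer that the error always favours the drug. Nothing in the documents supports that, because a change of modality could also produce a false early progression. This stands.
- **Contradiction with 3.7.9.1.** A reader might infer a plain conflict. However, 3.7.9 covers follow-up off treatment, while 3.8.4.2 covers patients still taking lapatinib, so the two can be read as separate groups. This stands in part: the text does not say which schedule governs a patient who has completed protocol therapy and continues lapatinib. The technique rule in 6.2.3.4 is unmet on either reading.
- **Size.** The 2-month illustration at 100% assumes that every event-free patient takes lapatinib, is followed by CT and has every event delayed, deaths included. This stands, so the figures are conditional. Larger figures need further assumptions. If half the events after 22.1 months were missed until month 48, a true 10.5 would read 12.7, but that supposes that no visit, deterioration or death registers in the meantime.

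**Conclusion.** The point holds in a limited form. Patients still at risk for the primary endpoint may be imaged by a modality to which one limb of the progression definition cannot be applied, and no rule bridges the two. The effect is on measurement consistency, in an uncertain direction.

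Its true size cannot be derived from the documents. Under the stated assumptions (exponential times, entry after 24 cycles, all later events 2 months late) the median rises by about 0.3 months at a true 10.5 or 0.5 months at a true 14, and proportionally less if CT use is partial. That is small against the trial's precision. The figures of 0.7 to 0.8 months require a move to lapatinib at 12 cycles, which the text does not state. The change is still worth making because it removes a site-dependent source of error from the primary endpoint at little cost.

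**What to change.** - In the Précis, 3.1, 3.8.4.2 and calendar footnote 11, state that progression in patients still at risk is assessed by MRI of the baseline site(s) with the baseline technique.
- Reconcile both modality and scan interval between those places and 3.7.9.1, and say which schedule applies to a patient continuing lapatinib. This point settles the modality only and does not propose an interval.
- In 6.2.3, state that where only CT is available the 25% size criterion is not scored from it, while a clear new lesion or clear worsening still counts.
- In section 8, add a sensitivity analysis that censors CT-followed patients without an event at their last MRI. It removes event-free time and keeps all events, so it can only lower the estimate. It should be read as a one-sided check.

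Cost: sites lose the convenience of CT, and there is slightly more analysis work. MRI is already the modality at baseline and on treatment, and entry required the ability to undergo it (2.1.1.4), although that does not guarantee it years later. Section 2.3 says accrual is closed, so the imaging rule would reach only remaining follow-up; the scoring rule and the sensitivity analysis can be applied to the analysis as a whole.

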## **3.9 SURGICAL THERAPY**

Not applicable in this protocol

## **4 CONCOMITANT MEDICATIONS/MEASURES**

### **4.1 SUPPORTIVE CARE**

All supportive therapy for optimal medical care will be given during the study period at the discretion of the attending physician(s) within the parameters of the protocol and documented on each site's source documents as concomitant medication.

**4.1.1 Anticonvulsants:** Antiepileptic medications should be used as indicated. However, only patients taking non-hepatic enzyme inducing antiepileptic drugs (non-EIAEDs) or no antiepileptic drugs are eligible to enroll on this trial. Patients must not be taking EIAEDs for at least 2 weeks prior to registration. See Appendix 12.2 for a list of EIAEDs and non-EIAEDs.

During therapy, patients who were previously on a non-EIAED and need to change anticonvulsants should be started on another non-EIAED if at all possible. No delays in treatment would be required.

If patients who were previously on no anticonvulsants require initiation of an anticonvulsant, a non-EIAED should be used if at all possible.

If a patient is started on an EIAED while on the study, he/she should immediately be started on another non-EIAED and the EIAED should be tapered and discontinued as quickly as possible. The patient may continue the lapatinib. The dates that the patient took an EIAED should be noted.

Patients who need to permanently change anticonvulsants but who cannot change to another non-EIAED will be taken off study.

- 4.1.2 Analgesics: As needed.
- 4.1.3 Hematopoietic Growth factors: Permitted for grade 4 neutropenia or neutropenia with fever and should follow American Society of Clinical Oncology guidelines for their use. [\*] Prophylactic use of growth factors is not allowed, nor can they be used to improve blood counts to allow initiation of treatment.
- 4.1.4 Treatment of rash: The acneiform rash associated with lapatinib treatment appears to be treatable with standard acne therapies, including topical and oral antibiotics used to treat acne. Anecdotal reports of improvement have occurred with any of the following: minocycline topical tetracycline, topical clindamycin, topical silver sulfadiazine, diphenhydramine, and oral prednisone (short course). Minocycline recommended dose: 200 mg po bid (loading dose), followed by 100 mg po bid for 7-10 days.
- 4.1.5 Nutritional Supplementation: Permitted.
- 4.1.6 Antacids: Permitted.
- 4.1.7 Calcium Supplements: Calcium supplements (e.g., calcium carbonate, 500 mg PO three times daily) may be required to maintain serum calcium levels above the lower limit of normal during chemotherapy treatment. Vitamin D supplements (e.g., ergocalciferol, 400 IU PO daily) may be appropriate for persistent hypocalcemia.
- 4.1.8 Anti-emetics/Anti-diarrheals: The nausea, vomiting, and diarrhea that may occur with lapatinib or temozolomide administration can generally be managed through the use of appropriate supportive measures [anti-emetics (e.g., 5-HT3 antagonists, benzodiazepines, prochlorperazine) and antidiarrheal medications (e.g., loperamide)]. Specific guidelines for the use of loperamide for the subacute (days after administration) form of irinotecan-induced diarrhea are provided below:
  - Patients should not be given drugs with laxative properties.
  - Loperamide should be started at the earliest sign of: (1) a loose stool, or (2) the occurrence of 1-2 more bowel movements than usual in 1 day, or (3) a significant increase in stool volume or liquidity. Loperamide should be taken in the following manner:
    - 4 mg at the onset of diarrhea and then 2 mg by mouth every 2 hours, around the clock until the patient is diarrhea free for at least 12 hours. Patients may take loperamide every 4 hours during the night.
  - Patients should increase fluid intake to help maintain fluid and electrolyte balance during episodes of diarrhea.

## **5 BIOSPECIMEN COLLECTION**

### **5.1 PATHOLOGY REVIEW**

#### **5.1.1 General Information**

Tissue evaluation is mandatory for this study. The evaluation will consist of confirmation that the histologic features meet WHO criteria for ependymoma, as well as an analysis of molecular markers MGMT methylation status. All blocks for review will be sent directly to [name].

### **5.1.2 Rationale**

The purpose of analyzing the tissue samples is to confirm the diagnosis of ependymoma, as well as to determine the status of key molecular markers. As described below, such markers will be examined in an effort to further characterize other factors that may be predictive of response and prognosis using the treatment regimens that are undergoing evaluation in this clinical trial. Furthermore, in the case where frozen tumor tissue is also available, more extensive genetic testing will be performed so that correlative profiles of gene expression to response and outcome can be made in this carefully studied, uniformly treated group of patients.

